3.7 UNANTICIPATED PROBLEMS REPORTING

The investigator will report unanticipated problems to the reviewing Institutional Review Board (IRB) and study sponsor. The UP report will include the following information:

- Protocol identifying information: protocol title and number, PI's name, and the IRB project number
- A detailed description of the event, incident, experience, or outcome
- An explanation of the basis for determining that the event, incident, experience, or outcome represents an UP
- A description of any changes to the protocol or other corrective actions that have been taken or are proposed in response to the UP

UPs that are serious adverse events (SAEs) or protocol violations will be reported to the IRBs within 7-10 working days of the investigator becoming aware of the event (see section 10.1.10 for individual IRB reporting timelines).

3.8 REPORTING UNANTICIPATED PROBLEMS TO PARTICIPANTS

Participants will be informed of any UP that changes the study's risk/benefit ratio and/or requires modification to the informed consent. The nature of the UP will determine how and when participants will be notified.

4 REGULATORY, ETHICAL, AND STUDY OVERSIGHT CONSIDERATIONS

4.1 INFORMED CONSENT PROCESS

Informed consent will be obtained for the Owete RCT participants and for participants of the qualitative focus groups and in-depth interviews to better understand mechanisms of the intervention action. Verbal

as well written consent forms will be utilized. Study team members will find a private place; carefully explain the nature and purpose of the study to each potential participant, potential risks and benefits, compensation for participation, and will describe the two study groups to which participants will be randomized. The consent process will be offered in English, Kiswahili, or Dholuo (as per the participant's preferences). Our study team has prior experience in obtaining informed consent for research and clinical trials within the cultural context of in Kenya. The informed consent procedure has been designed to maximize understanding of potential risks. Participants will be told that they may decline to participate at any point.

4.1.1 CONSENT/ASSENT

The following informed consent form (ICF) materials will be used in the main study:

- Phone study contact script (verbal)
- Eligibility screening consent (verbal)
- Census and screening form (written)
- Social network survey consent (written)
- Survey, HIVST, qualitative, medical record release, viral load, urine assay, and future contact consent form (written)
- Follow up survey, qualitative, medical record release, viral load, urine assay and future contact consent form (written)
- Promoter consent form (2 versions- control and intervention) (written)
- Photo consent forms

These consents are included as attachments to the protocol.

4.1.2 CONSENT PROCEDURES AND DOCUMENTATION

All consent forms will be translated into the local language and back translated into English to ensure correct use of language. Consent forms will be read aloud to participants by trained staff. The informed consent will describe the purpose of the study, all the procedures involved, and the risks and benefits of participation. Interviewers will ask participants to summarize the study and explain the reasons why they want to participate. Either a signature or a thumbprint (for those who cannot read) will be acceptable to confirm informed consent for participation in the study, in the case of written consent forms.

The process and timing of obtaining informed consent for study participation is detailed below:

1. Prior to the study start, we will conduct a pilot survey and qualitative interviews with potentially eligible men listed in the BMU census registry in the pilot site. If interested, study staff will administer a verbal script for informed consent, to screen men's potential eligibility to be in the pilot (the same screener used for the main study). Both the phone introduction and eligibility forms are verbal and included as attachments. The screening will be documented using a census and screening form, also attached. Following eligibility screening, written informed consent will be

obtained to enroll up to n=200 eligible men to participate in the pilot survey, using the pilot informed consent form. Some or all of these interviews may also be conducted over the phone, in response to the restrictions placed by the COVID-19 response efforts. For phone based data collection, we will include the phone data collection screening verbal script, a verbal consent for screening, and a verbal consent to participate-all of which are included as amendments to this protocol.

The in-person pilot activities will use the following forms (and their local-language versions):

- a. English phone screening script
- b. English census and screening form
- c. English verbal script for informed consent for study screening
- d. English written consent for pilot

The phone pilot activities will use the following forms (and their local-language versions):

- a. English pilot phone screening script
- b. English pilot screening form
- c. English verbal script for informed consent for study screening
- d. English verbal phone consent for study pilot
- 2. At study start, study team members will use a screening script, to introduce the study for potentially eligible men listed in the BMU census registry in the study sites. If interested, study staff will administer a verbal script for informed consent, to screen men's potential eligibility to be in the study. Both the phone introduction script and consent are verbal and included as attachments. The screening will be documented using a census and screening form, also attached. This will allow us to conduct these activities remotely, allowing for COVID-19 precautions.
- 3. After eligibility screening, written informed consent for the social network survey will be administered to up to n=1000 men to participate in the social network mapping process.
- 4. Within the first quarter of the study start, the network data will be analyzed and the sub-group of up to n=90 men who are socially connected, network central men will be selected for recruitment as promoters. Study staff will then obtain written informed consent from up to n=45 men in the intervention arm using the Informed Consent for Intervention Promoters and from up to n=45 men in the control arm using the Informed Consent for Control Promoters. This procedure will include consent to participate in trainings, to distribute information, HIVSTs (for intervention) and vouchers to peers in their networks, and to be contacted by study team members for follow up activities during the study period.
- 5. After the social networks are mapped, and clusters randomized to control or intervention, and promoters consented, written informed consent will be obtained to enroll up to n=>=1000 eligible men to participate in the study, using the *survey*, *HIVST*, *qualitative*, *medical record release*, *viral load*, *urine assay*, *and future contact consent* form. Potential participants will be presented and explained a consent form to participate in the baseline survey, 3 month follow up survey, qualitative interviews or focus group discussions if selected, contact for future research, as well as consent to use an HIVST. Further, this consent will ask for release of test dates, appointment dates, and medication information as well as other medical records. It will include permission for the use of the urine assay to test for PrEP adherence, if applicable and for those who are

subsequently identified as HIV-positive and enrolled in care, venous blood draws for viral load measurements during study scheduled visits. If verbally authorized, the viral load results may also be released to their provider to guide their care.

6. For men who receive a self-test and incentive voucher from a promoter (intervention) or a voucher for referral to the facility (control) but who were not part of the social network survey or the baseline survey consent procedures, we will consent them anew, following screening procedures similar to the baseline survey and study enrollment (men,_>=18 yrs., working in fishing related industries), and consent for the 3 month follow up survey, qualitative interviews or focus group discussions if selected, contact for future research. Further, this consent will ask for release of test dates, appointment dates, and medication information as well as other medical records. It will include permission for the use of the urine assay to test for PrEP adherence, if applicable, and for those who are subsequently identified as HIV-positive and enrolled in care, venous blood draws for viral load measurements.

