This study will leverage new technologies and insights from behavioral economics and social network research to test low-cost, scalable interventions to close gaps in the prevention and care cascade. To increase uptake of HIV testing and existing prevention and treatment services, we will test a strategy that recruits and trains highly-connected, network-central men to distribute HIV self-tests and provide linkage support to men in their close social networks. Men due to its convenience and privacy prefer HIVST.^{19,20} Policies are evolving rapidly, with WHO recommending HIVST scale-up and the Gates Foundation subsidizing self-test prices. Building on our studies of secondary distribution of self-tests by women,^{21,22} financial incentives,²³⁻²⁵ and adherence metrics²⁶⁻²⁹ to objectively assess outcomes, as well as other research demonstrating the importance of social networks for influencing norms and behaviors,³⁰⁻³⁸ we will evaluate an innovative social-network based approach to promoting HIV prevention and treatment behaviors among men. Network-central promoters – who are well positioned to disseminate information and influence behaviors – will distribute HIV self-tests, transport vouchers for referral services, and information on ART and PrEP, to men in their networks. Specifically, we will conduct a cluster-randomized trial of social network-based self-test distribution and linkage intervention among 80 close social networks of men in Kenya.

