8.2 SOCIAL NETWORK SURVEY

Visit 1 (recruitment/screening) for up to n=1800 men

Following community selection and preparation, the study team will conduct a Beach Management Unit (BMU) census/registry verification in study communities to identify the population of men eligible for the study. Tool for the baseline BMU Census/Registry data verification, updating and abstraction is included as appendix to this protocol. The study team will then screen, recruit and enroll up to n=1800 eligible men who give their informed consent to participate in the social network survey. Men who provide informed consent will be administered a social network survey that obtains information on the close social networks of fishermen. This module will ask participants to name the men in their community to whom they are most closely connected to for domains such as health (whom they would seek health information from or share information with), finances (to whom they would turn to borrow money), and spending time (on work and social activities). The social network data obtained in this way will enable us to determine the ties and close social networks that exist in the community, particularly among fishermen.

The social network survey is included as an attachment to this protocol.

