8.3 SOCIAL NETWORK MAPPING

After the social network survey data collection is completed, data will be analyzed and the close social networks of participants will be identified. These close social networks, clusters, will then be randomized 1:1 to intervention and control groups. Network-central, highly socially-connected men ("promoters") will be identified in each network group (one per group, with additional 'adjacent' alternates identified if primary potential promoters do not consent to participate as promoters). The study team will contact the potential promoters to administer informed consent to participate in the study as promoters; recruitment will proceed until at least n=45 and up to n=70 men in intervention, and at least n=45 and up to n=70 in control groups have been enrolled as promoters.

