1.2 SAMPLE SIZE DETERMINATION AND POWER CALCULATIONS

Aim 1

We calculate that the study will have an 80% or greater power to detect a significant difference in the proportion of HIV testing associated with the intervention arm, assuming a proportion self-testing in the control arm of 38% (observed data from SEARCH in fishermen) if the proportion testing in the intervention arm is 52% or greater (odds ratio of 1.8), calculated using an Intraclass Correlation Coefficient (ICC) of 0.15 (conservative based on SEARCH data), 70 clusters each in the intervention and control arms, average cluster size of 7 in both arms, and a type-1 error rate of 5%.^{125,126} Figure 2 shows statistical power and the range of detectable odds ratios over extremes of clustering effects.

Aim 2

For the Aim 2 combined primary outcome of successful linkage to ART or PrEP within 3 months of intervention start (+about 1 month), this study will have a 80% or greater power to detect a significant increase in successful linkage, assuming a proportion successfully linked at 3 months in the control arm of 24% (based on observed SEARCH trial linkage rates weighted for the number of eligible PrEP HIV-negative men and HIV-positive men not currently in HIV care) if the observed proportion in the intervention arm is 39% or greater (odds ratio of 2.0), using an ICC of 0.15, 70 clusters each in intervention and control arms, a cluster size of 7 in both arms, and a type-1 error rate of 5%. Statistical power for combined ART or PrEP

start is similar, with a reduction in anticipated eligible numbers per cluster reduced to 6 resulting in a small increase in the detectable odds ratio to 2.2 or greater. Power for a separate analysis of ART initiation alone is likely to be low given the small numbers of new HIV infections in the study sample with odds ratios in excess of three or four required.

Aim 3

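### The consent section limits promoters to 45 per arm, which allows at most 45 of the 70 networks per arm in the power section and takes Aim 1 power to about 73%

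*Protocol*

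**What the plan says.** The current protocol (version 11.0) gives different limits for the same quantities.

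**Promoters and networks**
- Section 4.1.2, item 4: a "sub-group of up to n=90 men who are socially connected" is selected for recruitment as promoters. The limit on consent is "up to n=45 men in the intervention arm using the Informed Consent for Intervention Promoters"; the control arm has an equal limit of 45.
- Section 8.3: recruitment of promoters runs until there are "at least n=45 and up to n=70 men in intervention", with the same range for control. There is one promoter per network.
- Section 8.5 trains as many as 140 promoters, and section 8.9 supports as many as 70 in the intervention arm.
- The synopsis (3.1) allows 140 clusters.
- Section 1.2 bases Aims 1 and 2 on "70 clusters each in the intervention and control arms".
- Section 4.1 (Study Rationale) speaks of "80 close social networks of men in Kenya". SAP section 11, written against protocol version 4.0, uses 40 clusters of 8 per arm.

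**Men in the network survey**
- Section 4.1.2, item 3: consent goes to "up to n=1000 men to participate in the social network mapping process".
- Section 8.2: "Visit 1 (recruitment/screening) for up to n=1800 men".

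Section 6.4 ties the two quantities together: a network can be randomized only if its promoter has consented.

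**The concern.** The figure of 45 promoters per arm is a floor in section 8.3 and a ceiling in section 4.1.2. Only exactly 45 per arm satisfies both. Because each network has one promoter and his consent is a condition of randomization, a ceiling on promoter consents is also a ceiling on networks.

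Section 4.1.2 sets out how many written consents staff obtain. Staff who follow it stop at 90 networks; staff who follow section 8.3 up to its maximum go beyond what 4.1.2 allows. What is at stake is whether the number of networks behind the stated 80% power can be reached under the consent procedure, and, if not, how much power is lost and for which aim.

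**Working it through.** **Inputs**
- Protocol 1.2: ICC 0.15, average network size m = 7, k = 70 networks per arm, type 1 error 5%. Aim 1: 38% against 52%. Aim 2: 24% against 39%.
- SAP section 16: two-sided tests.
- Protocol 4.1.2: at most 45 promoters per arm, hence k of at most 45.
- Networks are taken as equal in size, with no allowance for dropout, because section 1.2 states none.

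**Formulas**
- Design effect DE = 1 + (m − 1) × ICC = 1 + 6 × 0.15 = 1.90.
- Effective n per arm = k × m / DE.
- Power = Φ{ [ |p2 − p1| × √n − 1.96 × √(2 × p̄ × (1 − p̄)) ] / √( p1(1 − p1) + p2(1 − p2) ) }, where n is the effective n per arm and p̄ is the mean of p1 and p2.

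**The plan's own figure, Aim 1 at 70 per arm**
- p̄ = 0.45, so √(2 × 0.45 × 0.55) = 0.7036. Also √(0.2356 + 0.2496) = 0.6966.
- Effective n = 490 / 1.90 = 257.9.
- Power = Φ[ (0.14 × 16.06 − 1.96 × 0.7036) / 0.6966 ] = Φ(1.25) = 89%.

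Section 1.2 claims 80% or more, so its statement is met with room to spare. The odds ratio for 52% against 38% is 1.77, which agrees with the stated 1.8.

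**Aim 1 at the consent ceiling of 45 per arm**
- Effective n = 315 / 1.90 = 165.8.
- Power = Φ[ (0.14 × 12.88 − 1.379) / 0.6966 ] = Φ(0.61) = 73%.
- For 80% power, effective n = (1.379 + 0.8416 × 0.6966)² / 0.14² = 197.04, rounded up to 198. Networks per arm = 198 × 1.90 / 7 = 53.7, so 54. A continuity correction raises this to 58.
- At 45 per arm, the intervention proportion detectable with 80% power is about 53.3% (odds ratio 1.86).

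**Aim 2 at 45 per arm**
- p̄ = 0.315, so √(2 × 0.315 × 0.685) = 0.6569. Also √(0.1824 + 0.2379) = 0.6483.
- Power = Φ[ (0.15 × 12.88 − 1.2876) / 0.6483 ] = Φ(0.99) = 84%.

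| Networks per arm (size 7) | Effective n per arm | Aim 1 power | Aim 2 power |
|---|---|---|---|
| 70 (section 1.2) | 257.9 | 89% | 96% |
| 45 (section 4.1.2) | 165.8 | 73% | 84% |

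Other forms of the test hardly change Aim 1 at 45 per arm: 73.5% with an unpooled variance and 72.6% with a t reference distribution.

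**Mapping limit**
- 140 networks × 7 men = 980, which is fewer than 1000. The 1000-man limit is 800 below section 8.2, but it leaves numerical room for 140 networks of 7.

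**The case against.** The best reply is that the intended number is plain. The synopsis and sections 1.2, 8.3, 8.5 and 8.9 all agree on 70 per arm or 140 in total, and section 4.1.2 looks like text that was not updated when the trial grew. On that view this is a correction for consistency, not a flaw in the design. That stands as a description of the likely cause. It does not remove the contradiction, because 4.1.2 is operative text on how many consents may be taken.

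A second reply is that the loss is modest. Aim 2 stays above its stated 80%, and the proportion detectable in Aim 1 moves only from the stated 52% to about 53.3%. Both are true, and they limit the point to Aim 1. One might add that a one-sided test would give about 82% at 45 per arm. But the SAP specifies two-sided tests.

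Three stronger readings are tempting, and the documents do not support them:
- *The 1000-man limit also makes 140 networks impossible, or is the tighter constraint.* 980 men fit within 1000. Dividing 1000 baseline participants by 1800 mapped men does not give an expected yield either. Both figures are upper limits, and the protocol states no yield. Section 6.4 also builds networks from registry data as well as survey data, and section 6.5 does not require every member to take part.
- *Ninety networks of 7 are 630 men, below the synopsis minimum of 650.* Seven is a planning average and the synopsis says network size varies; 650 / 90 is only 7.2. The top of the synopsis range equals the survey number in 8.2, so the range may count mapped men rather than men in randomized networks.
- *The whole trial is underpowered.* Aim 2 is not. The Aim 3 calculation is stated in men on PrEP and ART, not in networks, so the effect of the ceiling on it cannot be read from the documents.

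**Conclusion.** The point holds for the promoter ceiling. As written, section 4.1.2 allows at most 45 + 45 = 90 networks against 140 in section 1.2: 50 fewer, or 36%. At that number Aim 1 has about 73% power instead of the stated 80% or more, and is 9 networks per arm short of the 54 that 80% requires. Aim 2 keeps about 84%. The survey-consent figure of 1000 is a separate contradiction with section 8.2 and does not by itself block the planned number of networks.

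This rests on one promoter per network (8.3), on promoter consent as a condition of randomization (6.4), on the planning values in section 1.2 and on two-sided testing. Unequal network sizes or loss to follow-up would lower every power figure here. The finding concerns what the text permits; the documents do not show how many promoters were in fact enrolled.

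**What to change.** 1. Amend section 4.1.2, item 3, to a limit of 1800 men in the network survey, and item 4 to a limit of 140 promoters, 70 per arm, so that both match sections 8.2, 8.3, 8.5 and 1.2.
2. In item 5 of the same section, the number of men to be enrolled is written as an upper and a lower limit at once. State which is meant.
3. Replace the figure of 80 networks in section 4.1 (Study Rationale), and align the 40 clusters of 8 per arm in SAP section 11 with the current protocol.
4. If 45 promoters per arm is the true limit, leave item 4 as it is. Instead restate section 1.2 for 45 networks per arm of 7, with about 73% power for Aim 1 and about 84% for Aim 2, and correct the larger figures elsewhere.

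The cost is a protocol amendment that changes figures, with the IRB approval that any amendment needs, and a matching SAP revision. Steps 1 to 3 add no men beyond those already planned in sections 8.2 to 8.5.

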Social network-based approaches show promise for generating positive social influence and accelerating health behavior change in men. The influence of social networks on health behaviors and outcomes is well established⁷⁸⁻⁸⁴ and it is known that social network characteristics can influence behavior through the circulation of ideas and social influence.⁸⁵ Network interventions are purposeful efforts to use networks to generate social influence, accelerate behavior change, and achieve positive health outcomes.⁸⁶⁻⁹¹ In SSA, prior research has shown the influence of social networks on HIV testing, ⁹²⁻⁹⁴ partner concurrency, ⁹⁵ and condom use.⁹⁶ Such an approach is further supported by research showing that behavioral and organizational change programs are most effective when implemented by members of the group undergoing the change, i.e., peers.^{97,98} We also now know that selecting influential nodes in a network (i.e. individuals who are highly connected) results in superior intervention effectiveness: selecting well-connected nodes, from a network perspective, are better than nodes chosen randomly, a finding demonstrated with simulations ^{99,100} and empirical examples.^{101,102} Thus, selecting highly socially connected men within social networks to act as 'promoters' may overcome long-standing barriers to HIV testing and uptake of additional health services.

To maximize the HIV prevention potential of HIVST, interventions are needed to promote linkage to care and prevention. As with strategies including home-based and community-based HIV testing, linkage rates following HIVST are often suboptimal without other interventions to motivate confirmatory testing and linkage to care and prevention. Given the absence of a counsellor during HIVST, it is arguably even more important to promote linkage interventions with HIVST. A recent WHO summary of the few HIVST studies conducted (usually without linkage interventions) reported that linkage after HIVST was 50-56% in general populations in SSA.⁷⁵ In its 2016 HIVST guidelines, WHO emphasized a need for evaluation of interventions to facilitate linkage to care and prevention. We will directly address this "Achilles heel" of HIVST with social network approaches and low-cost financial incentives, both intended to promote linkage to care.

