6.4 IDENTIFICATION OF CLOSE SOCIAL NETWORKS AND NETWORK-CENTRAL PROMOTERS

Using the social network data obtained from the baseline survey and BMU census/ registry data along with a name-matching algorithm, we will identify male close social networks that exist in study communities. Their defining characteristic will be that individual members of any given network will be connected to each other on multiple domains that indicate strong ties between them. Following the identification of distinct close social networks in communities, we will analyze the network data to determine a network-central individual having a high degree of connectedness across domains within each network. The network-central individual will be considered as the network-central 'promoter' of HIV testing and will be the main individual study staff will contact to implement intervention and control group activities and approached for consent. If a central individual is not interested in participation, we will approach the next most central individual. Local close networks with consenting promoters will be eligible for randomization.

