6.6 BASELINE SURVEY WITH MAPPED SOCIAL NETWORKS AND PROMOTERS SOCIAL NETWORKS

Based on men who have agreed to be in the study and were mapped to social networks and randomized, we will conduct a baseline survey with all network members and their central promoters. This baseline survey will include socio-demographic, health and sexual behaviors, including HIV testing history and will serve as the baseline for a number of measures prior to the study implementation.

The baseline survey is included as an attachment to this protocol.

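### Promoter consent is a precondition of randomising a network in one place and follows randomisation, by arm, in another; and the men in the Aim 1 primary comparison are not defined consistently

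*Protocol*

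**What the plan says.** **Order of promoter consent and randomisation.** Protocol 6.4 identifies a central man, moves to the next most central man if he declines, and concludes: "Local close networks with consenting promoters will be eligible for randomization". SAP 10 has the same sentence. Protocol 8.3 reverses this. After mapping, "These close social networks, clusters, will then be randomized 1:1 to intervention and control groups"; staff then contact potential promoters for consent, with "alternates identified if primary potential promoters do not consent to participate as promoters", and "recruitment will proceed until at least n=45 and up to n=70 men in intervention", with the same range for control. Protocol 4.1.2 item 4 takes consent from men already in an arm, for intervention "using the Informed Consent for Intervention Promoters" and for control on a separate form. Protocol 4.1.1 lists both versions.

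**Order of member consent.** Item 3 of Protocol 4.1.2 takes written consent to the network survey before mapping. Item 5 takes consent to the trial itself afterwards: "After the social networks are mapped, and clusters randomized to control or intervention, and promoters consented, written informed consent will be obtained to enroll" the members. Protocol 6.6 and 8.4 agree: among men who "were mapped to social networks and randomized, we will conduct a baseline survey".

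**Who is surveyed and who is analysed.**

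| Source | Men included |
|---|---|
| Protocol 6.7 | Randomised men who took the baseline survey, plus new men who received a self-test |
| Protocol 8.6 | All men mapped to a randomised network, plus unmapped men given a kit (intervention) or voucher (control), plus promoters |
| SAP 20, intent to treat | Everyone randomised, whether or not they received a kit; SAP 19 counts promoters as randomised |
| Protocol 1.3.2 | Participants as measured in the 3-month surveys, by randomised network arm, intent to treat |
| SAP 26 | Study participants at the 3-month visit |

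SAP 28 scores missing primary outcomes as failure. SAP 27f lists no sensitivity analyses.

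**The concern.** Both orders of promoter consent cannot be followed. Under Protocol 8.3 a candidate learns what his arm asks of him before he accepts. The tasks differ: intervention promoters hand out kits and transport vouchers and are offered further training, while control promoters hand out referral vouchers. Refusal, and so replacement by an alternate, can therefore differ by arm. The promoter delivers the intervention, so who fills the role is part of what each arm receives.

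The second issue is the denominator. Network membership is fixed before allocation, which is a strength. Joining the trial and taking the baseline survey come after allocation, and Protocol 6.5 lets a network be randomised without all its members taking part. A primary set limited to baseline-surveyed men is therefore formed after allocation, whereas one of all mapped men is not. Adding men whom promoters reached outside their networks would bring in people who were never randomised.

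**Working it through.** **Order.** No arithmetic applies. Protocol 6.4 and SAP 10 run: map, promoter consents, randomise. Protocol 8.3 runs: map, randomise, promoter consents or is replaced. Item 4 of Protocol 4.1.2 fits only the second, since consent is sought by arm. Nothing describes concealing the arm until consent. The documents give no promoter refusal rate, so the effect is not quantified.

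**The plan's own Aim 1 figure.** Inputs from Protocol 1.2: 38% vs 52%, 70 networks of 7 per arm, ICC 0.15; two-sided 5% from SAP 16. Design effect = 1 + (7 − 1) × 0.15 = 1.90. Effective n = 490 / 1.90 = 257.9 per arm. A pooled two-proportion z-test gives 89.4% power, so the stated 80% or greater holds.

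**Mapped men who never join, equally in both arms** (proportion d assumed; true rates 38% vs 52%).

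- Randomised set, missing = failure: difference = 0.14 × (1 − d), n = 490, design effect 1.90.
- Baseline-surveyed cohort: difference stays 0.14; n = 490 × (1 − d); design effect = 1 + (7(1 − d) − 1) × 0.15.

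| d | Randomised set | Surveyed cohort |
|---|---|---|
| 10% | 34.2% vs 46.8%, 12.6 points, power 83% | n = 441, design effect 1.795, 14.0 points, power 88% |
| 20% | 30.4% vs 41.6%, 11.2 points, power 76% | n = 392, design effect 1.69, 14.0 points, power 86% |

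**Refusal in one arm only, no true effect** (38% in both arms; 10% of the named group declines, assumed).

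- Non-testers decline. Cohort: 0.38 / (0.38 + 0.62 × 0.9) = 0.405, a false difference of 2.5 points, rejected 8.9% of the time. Randomised set: 0 points.
- Would-be testers decline. Cohort: 0.342 / (0.342 + 0.62) = 0.3555, a false difference of 2.4 points, rejected 8.8% of the time. Randomised set: 0.38 − 0.342 = 3.8 points, rejected 14.6% of the time.

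So each set is worse in one of the two cases.

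**Illustration only: unmapped men pooled.** Assume that 10%, 20% or 30% of the 70 × 6 = 420 kits meant for others correspond to added men, so m = 42, 84 or 126 per arm. Design effect = 1 + ((490 + m)/70 − 1) × 0.15 = 1.99, 2.08, 2.17. With no effect in mapped men, the false difference is m(a − b)/(490 + m), where a and b are the assumed testing rates among added men in intervention and control.

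| Assumption | m = 42 | m = 84 | m = 126 |
|---|---|---|---|
| a = 90%, b = 50%: false points (rejection) | 3.2 (11.5%) | 5.9 (28.4%) | 8.2 (50.1%) |
| a = 90%, b = 70%: false points (rejection) | 1.6 (6.6%) | 2.9 (10.6%) | 4.1 (16.4%) |
| True 38% vs 52%, a = b = 70%: points (power) | 12.9 (85%) | 12.0 (80%) | 11.1 (76%) |

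Equal rates with no true effect give 0. Pooling can thus inflate or dilute, depending wholly on rates that the documents do not give.

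**The case against.** Several stronger readings are tempting, and the documents do not support them.

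- *All member consent follows allocation.* It does not: network-survey consent comes first, and members in both arms sign one common form.
- *The SAP ignores members who do not take part.* SAP 10 says full participation is not required, and SAP 24 reports withdrawals by arm and beach. What is missing is a rule for the denominator.
- *The 3-month sample is plainly not the randomised set.* Protocol 8.6 puts no baseline-survey condition on mapped men; with promoters, that is close to SAP 20. The fault is inconsistency with Protocol 6.7.
- *Unmapped men will be pooled.* Protocol 1.3.2 with SAP 20, read plainly, excludes them, and Protocol 6.7 describes data collection. Kit numbers follow the map (Protocol 8.5), promoters are told to stay within their network (Protocol 9.2, SAP 10), and network numbers are printed on kits and vouchers. Still, Protocol 8.6 calls these men study participants, the term SAP 26 uses for its denominator, and no sentence keeps them out.
- *Replacement promoters would be weaker.* The background remark that "selecting well-connected nodes, from a network perspective, are better than nodes chosen randomly" compares central men with random ones. Replacements here are the next most central or adjacent men, so it says nothing about the size of any loss.
- *Baseline must precede randomisation.* The current protocol consistently places it after. SAP 9 appears to differ, but it was written for Protocol 4.0, and Protocol 6.3 also calls the network survey a baseline survey. Reversing this would be a redesign.

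It is also fair to say that arm-specific promoter forms reflect different duties, and that the randomised set costs power and counts as failures men who never joined the trial. Both stand and bear on the fix. None of these points resolves the contradiction over promoter consent.

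**Conclusion.** The contradiction over promoter consent is certain from the text. Followed as written, Protocol 8.3 lets promoter selection depend on arm. That is a risk of selection bias, not a demonstrated one, and its size cannot be derived from the documents.

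The Aim 1 denominator needs to be stated. The choice matters moderately under assumed refusal: about 5 points of power at 10% non-joining and 10 at 20% between the two candidate sets, and false differences of roughly 2 to 4 points if 10% of testers or non-testers decline in one arm only. Neither set is protected in every case. The randomised set is preferable as primary because its membership is fixed before allocation and it is what SAP 20 already says, not because it is always less biased. The pooling figures only illustrate why an explicit exclusion is worth a sentence. The point should be fixed; it does not invalidate the trial.

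**What to change.** 1. Amend Protocol 8.3 and 4.1.2 item 4 to the order in Protocol 6.4 and SAP 10: for any network not yet allocated, promoter consent is obtained before the arm is known. A single arm-neutral form is one way to do this. For networks already allocated, report promoter refusals and replacements, and member non-enrolment, by arm.
2. State in Protocol 1.3.2 and SAP 20 and 27 that the Aim 1 primary comparison is all men mapped to a randomised network before allocation, promoters included, analysed by network arm, with missing outcomes handled as in SAP 28. Add the baseline-surveyed cohort of Protocol 6.7 as a sensitivity analysis in SAP 27f, and note that neither set is neutral if refusal differs by arm. Confirm that network-survey consent covers counting mapped men who later decline.
3. Keep men first enrolled at 3 months out of the primary comparison and report them separately, by the promoter's arm, as spillover.

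**Cost.** Items 2 and 3 are text and table rows; the three groups already have separate 3-month survey versions. The price of item 2 is dilution, 14 to 12.6 points at 10% non-joining, which the sensitivity analysis makes visible. Item 1 is probably text and reporting only: Protocol 8.7 ends 6-month abstraction in June 2023, so a network starting after about December 2022 could not reach 6 months, and protocol version 11.0 is dated 29 November 2022.
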